2.2.1. Objectives

2.2.1.1. **Primary Objective**

• To evaluate the effect of lumasiran on the percent change in urinary oxalate excretion

2.2.1.2. Secondary Objectives

- To evaluate the percentage of patients who achieve a $\geq 20\%$ reduction in 24-hour urinary oxalate with lumasiran
- To evaluate the effect of lumasiran on urinary calcium oxalate supersaturation

2.2.1.3. Exploratory Objectives

- To evaluate the effect of lumasiran on absolute levels of urinary oxalate excretion
- To evaluate the effect of lumasiran on the occurrence of kidney stones
- To evaluate additional PD parameters of plasma oxalate, plasma glycolate, and urinary glycolate
- To characterize PK of lumasiran
- To assess for antidrug antibodies (ADA) against lumasiran
- To evaluate the effect of lumasiran on spot urinary oxalate:creatinine ratios
- To evaluate the effect of lumasiran on maintaining 24-hour urinary oxalate ≤upper limit of normal (ULN) over time
- To evaluate the effect of lumasiran on maintaining a 25% reduction in urinary calcium oxalate supersaturation over time
- To evaluate the effect of lumasiran on 24-hour urinary oxalate excretion after Month 6
- To evaluate the effect of lumasiran on estimated glomerular filtration rate (eGFR)
- To evaluate the effect of lumasiran on patient healthcare resource utilization
- To assess the impact of kidney stone events on patient-reported pain and quality of life (QoL)

2.2.1.4. Safety Objective

• To evaluate the safety and tolerability of lumasiran

2.2.2. Endpoints

2.2.2.1. Primary Endpoint

• Percent change in 24-hour urinary oxalate from baseline to Month 6 (average across Months 4 through 6)

2.2.2.2. Secondary Endpoints

- Percentage of patients who achieve a ≥20% reduction in 24-hour urinary oxalate from baseline to Month 6 (average across Months 4 through 6)
- Percent change in urinary calcium oxalate supersaturation from baseline to Month 6 (average across Months 4 through 6)

2.2.2.3. Exploratory Endpoints

- Absolute change in 24-hour urinary oxalate from baseline to Month 6 (average across Months 4 through 6)
- Incidence rate of clinical and radiographic kidney stone events
- Time to first kidney stone event
- Change from baseline in plasma oxalate
- Change from baseline in plasma glycolate
- Change from baseline in urinary glycolate
- Plasma PK of lumasiran
- ADA frequency and titer
- Change from baseline in spot urinary oxalate:creatinine ratios
- Percentage of patients with 24-hour urinary oxalate \leq ULN over time
- Percentage of patients having a 25% reduction in urinary calcium oxalate supersaturation over time
- Change from baseline in 24-hour urinary oxalate excretion after Month 6
- Change from baseline in eGFR
- Kidney stone event related hospitalizations, emergency room visits, unscheduled office visits, or procedures
- Patient-reported severity and symptomatic and functional impact of kidney stone events

2.2.2.4. Safety Endpoint

• Frequency of AEs

2.3. Study Procedures

The Schedule of Assessments from the protocol is included as Section 7.1.

2.4. Randomization Methodology

Patients will be randomized 1:1:1 to receive lumasiran 284 mg, lumasiran 567 mg, or placebo in a DB manner. Stratification will be performed at randomization according to baseline urinary oxalate level ($\leq 1.25 \times ULN \text{ vs} > 1.25 \times ULN$) from the mean of the first 2 valid 24-hour urine collections and the number of historical kidney stone events in the 12 months prior to screening ($\leq 1 \text{ vs} > 1$).

For stratification, a historical kidney stone event is defined as:

- the visible passage of a kidney stone
- a procedural intervention for removal of an asymptomatic or symptomatic stone

- if more than 1 stone was removed in a given procedure, this counts as 1 event unless bilateral ureteral stones were removed, in which case this counts as 2 events
- if more than 1 procedure was required to remove a single stone, this counts as 1 event
- a new (≥1 mm) or enlarged (by ≥2 mm) kidney stone on computed tomography (CT) imaging
 - it must be evident from the CT scans that the new or enlarged kidney stone event occurred during the 12 months prior to screening
 - if a procedure was performed to remove the stone(s) identified by CT, then only the procedure will be counted to avoid double counting the same stone.

2.5. Blinding

The randomization schedule is maintained by the interactive response technology (IRT) vendor. Alnylam is unblinded throughout the entire study. However, during the 15-month DB treatment period, investigators, site personnel, patients, and selected vendor personnel as outlined in the Randomization and Blinding Plan (RBP), will remain blinded to treatment assignment and any clinical laboratory results that could potentially unblind them, including PK data, ADA, and PD data (post-baseline results for 24-hour urinary oxalate, spot urinary oxalate:creatine, plasma oxalate, plasma and urinary glycolate, urinary calcium oxalate supersaturation), until study unblinding which will occur after all patients have completed Month 15 visits.

Unblinding is only to occur in the case of patient emergencies, or when necessary from a regulatory reporting perspective (eg, Suspected Unexpected Serious Adverse Reaction [SUSAR]), or after all patients have completed the 15-month DB treatment period and the unblinding authorization has been executed.

Details about the specifics of the blinding aspects for the study are outlined in the RBP.

2.6. Determination of Sample Size

The planned enrollment for this study is 120 patients.

The study is powered to detect a difference in urinary oxalate excretion between each lumasiran group and the placebo group. Assuming a standard deviation of 45% in the percent change from baseline in 24-hour urinary oxalate levels at Month 6, a sample size of 40 patients per group will enable a power of at least 80% in detecting a treatment difference of 30% between the treatment groups at a 2-sided significance level of 0.05. Table 1 shows the statistical power under various assumptions for a sample size of 40 per group.

Assumed standard deviation (SD)	Assumed difference (lumasiran – placebo)	Power
250/	20%	94%
2370	30%	99%
200/	20%	84%
50%	30%	99%
450/	20%	50%
4.370	30%	84%

Table 1: Sample Size Power Calculation	Table 1:	Sample Size Power Calculation	ons
--	----------	-------------------------------	-----

Abbreviations: SD=standard deviation

No multiplicity adjustment is considered in the sample size calculation.

3. ANALYSIS POPULATIONS

The populations (analysis sets) are defined as follows:

- Full Analysis Set (FAS): All randomized patients who received at least 1 dose of study drug. Patients in the FAS will be analyzed according to the randomized treatment arm.
- Safety Analysis Set: All patients who received at least 1 dose of study drug. Patients in the Safety Analysis Set will be analyzed according to the treatment actually received.
- PK Analysis Set: All patients who received at least 1 full dose of study drug and have at least 1 post-dose blood sample for PK parameters and have evaluable PK data.
- Plasma Oxalate Analysis Set: All patients who received at least 1 dose of study drug and have a baseline plasma oxalate level ≥1.5 times the lower limit of quantification/detection (LLOQ). The LLOQ of the plasma oxalate assay is 5.55 µmol/L. Because it is not possible to quantify plasma oxalate levels below LLOQ using the assay, patients with baseline plasma oxalate levels near the LLOQ (ie <1.5*LLOQ) are excluded from the analysis to ensure that meaningful reductions in plasma oxalate can be evaluated for the study population.

The primary population used to evaluate efficacy will be the FAS. Safety will be analyzed using the Safety Analysis Set. The PK Analysis Set will be used to conduct PK analyses. Both the FAS and Safety Analysis Set will be used to summarize demographic and baseline disease characteristics. The Safety Analysis Set will be used for medical history, prior and concomitant medications, and protocol deviations. The Plasma Oxalate Analysis Set will be used to evaluate the endpoint for the change from baseline in plasma oxalate.

4. GENERAL STATISTICAL CONSIDERATIONS

Statistical analyses will be conducted using SAS software Version 9.4 or newer or R version 3.6 or newer.

4.1. General Considerations

Categorical variables will be summarized using counts and percentages. The percentage will not be presented for a count of zero.

Continuous variables will be summarized using the following descriptive summary statistics: number of patients (n), mean, standard deviation (SD), standard error of the mean (SEM), median, first quartile (Q1), third quartile (Q3), minimum, and maximum. The same level of precision collected in the database will be displayed for the minimum and maximum, plus one additional decimal for the mean and median, plus 2 additional decimals for SD and SEM.

For 24-hour urinary oxalate, urinary calcium oxalate supersaturation, and 24-hour urinary glycolate:creatinine ratios, the median of valid collections will be used as the value at any visit where multiple collections are done because of the variability of these parameters. For other PD parameters, the mean of all assessments will be used if multiple collections are done at a given visit. For safety laboratory parameters, assessments collected and recorded as lower than the LLOQ will be replaced by the LLOQ. Any assessment collected and recorded as greater than the upper limit of quantification (ULOQ) will be replaced by the ULOQ. The day of the first dose of study drug administered is defined as Day 1. The Study Day of a time point of interest is calculated as follows.

If on or after Day 1, Study Day = date of interest – date of the first dose of study drug + 1

If prior to Day 1, Study Day = date of interest – date of the first dose of study drug

There is no Day 0. For example, the day before the first study drug dose is defined as Day -1.

All descriptive summaries will be presented by treatment arm (lumasiran 284 mg, lumasiran 567 mg, placebo) and overall, where applicable. In addition to presentation by treatment arm, a pool of lumasiran 284 mg and 567 mg will also be presented as all lumasiran treatment for the safety analysis.

4.2. Multiple Comparisons/Multiplicity Procedure

No multiplicity adjustment is planned.

4.3. Handling of Missing Data

No explicit imputation will be done for missing values for the analyses of the primary, secondary, or exploratory endpoints. For all analyses using mixed-effect model for repeated measures (MMRM), the model makes use of all available data, including patients with partial data (i.e., with missing data), to estimate the mean treatment effect without employing formal imputation.

4.4. **Baseline Definitions**

Baselines for efficacy parameters are defined as follows:

- For 24-hour urinary oxalate, urinary calcium oxalate supersaturation, and 24-hour urinary glycolate:creatinine ratios, baseline will be defined using the median value from all valid 24-hour urine collections obtained prior to the date of the first dose of study drug.
- For other PD parameters, baseline will be defined as the mean of all measurements collected prior to the first dose of study drug.

For laboratory parameters and vital signs, baseline will be defined as the last non-missing value available (scheduled and unscheduled) prior to the date and time of the first dose of lumasiran.

4.5. Randomization Stratification Factors

The baseline urinary oxalate level ($\leq 1.25 \times ULN \text{ vs} > 1.25 \times ULN$) from the mean of the first 2 valid 24-hour urine collections and the number of historical kidney stone events in the 12 months prior to screening ($\leq 1 \text{ vs} > 1$) will be used as stratification factors. These stratification factors are recorded in both the IRT and the clinical database. In statistical analyses that use randomization stratification factors as covariates, the stratum assignment will reflect the values as recorded in the clinical database (EDC). In the presence of stratification errors, the stratification used in analysis may not match that in the IRT. A comparison of the number and percentage of patients in each randomization stratification factor in IRT versus the clinical database will be summarized by randomized treatment arm and overall.

4.6. Planned Analyses

The primary analysis will be performed after all randomized patients have completed the Month 6 visit or discontinued from the study. For the primary analysis, as this study will be ongoing with some patients in the 9-Month Treatment Extension Period, the study database will be locked with all data up to a prespecified cutoff date quality controlled, ie, data in the EDC system will be cleaned and frozen and external laboratory data will be cleaned and quality controlled (and quality assured, where appropriate).

The primary analysis will include data on or prior to this prespecified cutoff date. For the efficacy summaries, all data up to and including the Month 6 visit will be presented. For assessments with start and end dates (eg, AEs, medications), the start date will be compared with the pre-specified cutoff date. Data records with start dates after the specified data cutoff date will be excluded.

The final analysis will be conducted after all patients have completed the Month 15 visit or discontinued from the study. The database will undergo a final lock.

Additional details regarding the database lock process are located in the study Data Management Plan.

4.7. Visit Windows

For PD and safety parameters, no window rules will be implemented, and the reported eCRF visits will be used for analysis.

The following general conventions for unscheduled assessments will apply unless otherwise specified:

- If by-visit summaries are based on CRF Visit, only scheduled assessments will be included in by-visit summaries. Unscheduled assessments will not be included.
- Unscheduled assessments will be used in the calculation of baseline values and for shift from baseline to worst post-baseline tables. They will also be included in by-patient listings and spaghetti plots.

5. STATISTICAL ANALYSES FOR THE DOUBLE-BLIND PERIOD

5.1. Patient Disposition

The number and percentage of patients in the following categories will be summarized by treatment arm and overall, for the FAS and Safety Analysis Set:

- Randomized
- Treated
- Completed the Month 6 visit
- Completed treatment
- Completed the study
- Discontinued treatment and primary reason for discontinuation of treatment
- Withdrew from study and primary reason for withdrawal from study

A patient is defined as having completed the Month 6 visit if the patient has any of the assessments required for the Month 6 visit.

The number and percentage of patients who met criteria for the FAS, Safety Analysis Set, and PK Analysis Set will be summarized by all randomized patients.

The number and percent of patients enrolled by country and site will be summarized by randomized arm and overall.

Screen failures and the reason for screen failure will be summarized by all screened patients.

A data listing for treatment/study completion information along with the primary reasons for treatment discontinuation and/or study withdrawal will be generated.

5.2. Demographics and Baseline Characteristics

Demographic and baseline disease characteristics will be summarized by treatment arm and overall using the FAS and Safety Analysis Set, and also presented in listings.

Demographic characteristics including age at screening (years), height (cm), weight (kg), and body mass index (BMI [kg/m²]) will be summarized using descriptive statistics. Age group (18 to <65, \geq 65), sex, race, ethnicity, and region (US, Europe) will be summarized by presenting the frequencies and percentages of patients in each category.

Baseline disease characteristics including 24-hour urinary oxalate excretion (mg/24hr), urinary calcium oxalate supersaturation (DG), plasma oxalate (μ mol/L), plasma glycolate (μ mol/L), 24-

hour urinary glycolate:creatinine ratios (mmol/mmol), spot urinary oxalate:creatinine ratios (mmol/mmol), and eGFR (mL/min/ $1.73m^2$) will be summarized by descriptive statistics. Heterozygosity for any *AGXT* mutation (Yes/No) will be summarized by the number and percentage of patients in each category.

A tabulation of historical kidney stone events that occurred within 5 years prior to screening and within 12 months prior to screening will be presented. The number of kidney stone events will be summarized using descriptive statistics. Additional characteristics will be summarized by presenting the numbers and percentages of patients in each category:

- Patients with at least one kidney stone event (visible passage of kidney stones, a procedural intervention for removal of an asymptomatic or symptomatic stone, a new or enlarged kidney stone on CT imaging)
- Patients with at least one kidney stone event related hospitalizations, emergency room visits, urgent care, or urgent/unscheduled office visits
- Patients with a stone composition >50% calcium oxalate from the 2 most recently analyzed kidney stones (Yes/No)
- Patients for whom only 1 kidney stone was available for composition analysis

5.3. Medical History

Medical or surgical history will be coded using the Medical Dictionary for Regulatory Activities (MedDRA), version 24.1 or newer. Unique patients who report medical history events will be summarized and listed for the Safety Analysis Set by MedDRA system organ class (SOC), high level term (HLT) and preferred term (PT).

5.4. Protocol Deviations

Protocol deviations will be classified by medical review prior to the 6-month primary analysis and prior to the FA database lock. Major protocol deviations will be identified in the protocol deviation file. A major protocol deviation is a deviation that may significantly impact the completeness, accuracy, and/or reliability of the trial data; that may significantly affect a subject's rights, safety, or well-being (ICH E3 R1 Structure and Contents of Clinical Study Reports Guidance for Industry, 2013).

The Sponsor or designee will be responsible for producing the protocol deviation file. This file will include a description of each protocol deviation and whether each deviation is classified as major. The file will be reviewed and finalized prior to the 6-month primary analysis database lock and prior to the FA database lock.

All protocol deviations and major protocol deviations will be summarized and listed for the Safety Analysis Set.

5.5. Study Drug Exposure and Compliance

The following variables will be summarized by descriptive statistics and/or frequency tabulation for the Safety Analysis Set:

- Duration of study drug exposure (months), defined as: (date of last exposure date of first dose +1)/30.44. Date of last exposure is the earliest date of the following:
 - date of last dose + 168 days (eg, the length of the longest dosing interval)
 - date of end of study
 - date of data cutoff for the analysis
- Cumulative study drug exposure time (patient-years)
- Number of patients on study drug for ≥ 1 day, ≥ 3 months, ≥ 6 months
- Number of doses received as continuous and categorical variables (1, 2, or 3)
- Cumulative number of doses received
- Number of missed doses (0, 1, 2, or 3) as a categorical variable
- Total study drug exposure (mg) as a continuous variable
- Total volume administered (mL)

5.6. **Prior and Concomitant Medications**

Medications will be coded using the World Health Organization (WHO) Drug Dictionary, version B3 WHO Drug Global - Sep 2018 or newer. Unique patients who reported medications will be summarized by Anatomical Therapeutic Chemical (ATC) level 3 class (or level 2 if not available) and PT. Summaries and listings for the Safety Analysis Set will be provided for prior and concomitant medications separately.

Prior medications are defined as medications with start date and stop date prior to the first dose of study drug. Concomitant medications are medications, other than the study drug, administered on or after the first dose date of study drug, as well as medications that started prior to the first dose of study drug and are ongoing after the first dose of study drug. If medication start date is on or after the date of first dose of study drug, the medication will be summarized as a concomitant medication even if the medication end date is missing. If the end date of a medication is missing or incomplete such that it cannot be determined whether it is after the first dose of study drug, it will be counted as a concomitant medication.

For missing or partial dates for medications, the imputation of start and end dates is described in Section 7.3.

5.7. Efficacy Analyses

5.7.1. **Primary Endpoint(s)**

5.7.1.1. Definition of Estimand

For the primary objective of evaluating the efficacy of the study drug lumasiran compared with placebo on the percent change in urinary oxalate excretion, the primary estimand is defined as follows:

- **Target population**: Patients with recurrent calcium oxalate kidney stone disease and elevated urinary oxalate levels.
- **Treatment condition**: Lumasiran 284 mg, lumasiran 567 mg, or placebo administered by SC injection at Day 1, Month 3, and Month 9
- Endpoint: the percent change in 24-hour urinary oxalate from baseline to Month 6 (average across Months 4 through 6)
- **Population-level summary**: the least square (LS) mean difference in percent change in 24-hour urinary oxalate from baseline to Month 6 (average across Months 4 through 6) between each lumasiran dose group and the placebo arm.

• Strategies for intercurrent events (ICE):

Table 2: Intercurrent Event Strategies for the Primary Analysis of Primary Endpoint

Intercurrent Event	Strategy with Rationale
Selected medication of vitamin C equivalence ¹	Hypothetical strategy: 24-hour urinary oxalate collection will be excluded from the analysis if dose of vitamin C equivalent to \geq 500 mg in a single day is taken at any point within 4 days prior to the start of or during the urine collection. Rationale: vitamin C can be converted to oxalate, confounding urinary oxalate measurement.

¹ To identify vitamin C equivalence, two Alnylam physicians will each conduct an independent review of the concomitant medications to identify medications containing vitamin C. If there are any discrepancies, a meeting will be held to reach a consensus on each discrepancy. Once the medications are identified, the Alnylam DSS team will programmatically identify the total dose of vitamin C taken in a single day.

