# 3.5. Blinding

Site personnel and patients will be blinded to study drug treatment; site personnel preparing study drug may be unblinded to study drug treatment only where required by documented institutional procedure. The Sponsor will have access to unblinded study data during the conduct of the study. Lumasiran and placebo will be packaged identically and will be administered at the same volume under the supervision of the Investigator at the study center or by a healthcare professional at the patient's home (see Section 5.2.2). Since lumasiran may be visually

distinguishable from placebo, the syringe will be masked prior to administration by a healthcare professional. See the Pharmacy Manual for additional details.

All site personnel will be blinded to laboratory results of oxalate, calcium oxalate supersaturation, and glycolate from after the time of the first dose until unblinding. Results will not be reported to the Investigator from the first dose until the last patient completes assessments at the Month 15 visit. In addition, Investigators and staff involved with this trial and all medical staff involved in the patient's medical care should refrain from obtaining measurements for oxalate, calcium oxalate supersaturation, or glycolate from the first dose until the sites and patients are unblinded, or until the patient ends the study, whichever is earlier. If oxalate, calcium oxalate supersaturation, or glycolate are measured during the blinded period, all reasonable steps must be undertaken to avoid informing the patient and site personnel of the results until the sites and patients are unblinded.

Any unplanned unblinding occurring during the study period will be documented and reported in the clinical study report.

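### Do the unstated details of the vitamin C product review, and of an unrepeated invalid Month 3–6 urine collection, put the primary analysis at risk?

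*SAP*

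**What the plan says.** **Vitamin C rule.** Vitamin C is the only intercurrent event in SAP Table 2, and it is handled by a hypothetical strategy. Dose and time window are fixed. On which products count, the footnote says "two Alnylam physicians will each conduct an independent review of the concomitant medications to identify medications containing vitamin C"; disagreements go to a consensus meeting, and daily totals are then computed by program. SAP 5.7.1.3 adds a sensitivity analysis that keeps all the data.

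**Blinding.** Protocol 3.5 says "The Sponsor will have access to unblinded study data during the conduct of the study", and SAP 2.5 says "Alnylam is unblinded throughout the entire study". SAP 2.5 also says "Details about the specifics of the blinding aspects for the study are outlined in the RBP"; that Randomization and Blinding Plan (RBP) was not supplied. For a different file, the protocol deviations, SAP 5.4 does set a completion point: "The file will be reviewed and finalized prior to the 6-month primary analysis database lock and prior to the FA database lock".

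**Medication classes (SAP 5.6).** "Prior medications are defined as medications with start date and stop date prior to the first dose of study drug", whereas "Concomitant medications are medications, other than the study drug, administered on or after the first dose date of study drug", together with those still ongoing after it. A medication whose end date is too incomplete to place counts as concomitant.

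**Baseline (SAP 4.4).** For urinary oxalate, "baseline will be defined using the median value from all valid 24-hour urine collections" taken before the first dose. No vitamin C exclusion is mentioned there.

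**Invalid collections.** Protocol Table 4 schedules one collection at each of Months 3 to 6, with one supervised repeat if it is invalid. Protocol 6.2.1.1 applies the validity criteria throughout the study, and invalid samples are still sent for assay. SAP 4.1 takes the median of valid collections where a visit has several. SAP 4.3 does no explicit imputation.

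**The concern.** A reader sees an unblinded sponsor whose own physicians decide which products trigger removal of primary-endpoint values, with no stated masking and no date by which the list closes. If the list could be shaped with knowledge of arm or oxalate result, the exclusions could favour a lumasiran arm and the type I error would no longer be 5%.

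Two further points concern which values enter. A product stopped before Day 1 is prior medication, so the footnote read literally does not review it, although Table 2 is worded for any collection and baseline comes from screening collections. The all-data sensitivity analysis would not reveal this, because the same baseline enters both analyses. And an invalid Month 3–6 sample still yields an oxalate value. Read literally, two invalid samples at a visit leave a missing value, while a single unrepeated one might be used.

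**Working it through.** **Planning figures.** SAP 2.6 gives 40 patients per group, SD 45, difference 30, two-sided 0.05. The exact noncentral t gives 83.8% power, matching the stated 84%. Standard error of a difference: 45 × √(2/40) = 10.06 points. None of the three points alters these inputs.

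**1. Selective exclusion in one arm.** One arm has 40 × 3 = 120 collections over Months 4–6. Take 45 as the SD of a single collection (an assumption; the shifts scale with it). Removing k collections that lie D above the arm mean lowers that mean by k × D/(120 − k). Type I error is P(|Z + d| > 1.96), where d is the shift divided by 10.06.

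| k | D | Shift (points) | d | Type I error |
|---|---|---|---|---|
| 1 | 45 | 45/119 = 0.38 | 0.038 | 5.02% |
| 3 | 45 | 135/117 = 1.15 | 0.115 | 5.15% |
| 6 | 45 | 270/114 = 2.37 | 0.235 | 5.64% |
| 6 (the highest) | 2.06 × 45 = 92.7 | 556/114 = 4.9 | 0.485 | about 7.7% |

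The first three rows are illustrations, not bounds. The last takes the mean of the top 5% of a normal distribution, about 2.06 SD. It would require the six highest values in one arm all to fall under the rule. The rule does not allow that choice. A collection leaves only if the patient's own record shows at least 500 mg in the window, and a listed product counts in every arm.

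**2. Inflated baseline.** Let a share f of every arm have baseline too high by a factor b, with a true 30% reduction on lumasiran. Observed difference: −30 × (1 − f + f/b). Placebo shift: 100 × f × (1/b − 1). The documents give no rate, so f and b are assumptions.

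| f | b | Difference | Placebo shift |
|---|---|---|---|
| 1% | 1.111 | −29.97 | −0.1 |
| 5% | 1.25 | −29.7 | −1.0 |
| 10% | 1.5 | −29.0 | −3.3 |

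The factor 1.111 comes from the screening variability rule (Protocol 6.2.1.2). If one of two collections is inflated by c and the other is at its true value, (c − 1)/((1 + c)/2) = 0.20 gives c = 1.222 and b = (1 + 1.222)/2 = 1.111. Above that, a third collection is requested.

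For the 20% responder endpoint, a patient with true reduction r is falsely counted if b ≥ (1 − r)/0.80. That is 1.25 with no true change and 1.125 with a true 10% reduction.

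The plan also limits how often this can arise. Inclusion criterion 5 holds vitamin C supplements below 200 mg daily. Criterion 6 requires medications that alter urinary oxalate to be stable for at least 60 days before randomisation, and screening collections fall within a 60-day period. Dietary compliance is itself a validity criterion. Any remaining effect arises before randomisation and is balanced across arms in expectation.

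**3. A lone invalid value, kept.** Suppose invalid samples are 30% under-collected, with rates v_P on placebo and v_L on lumasiran (assumptions). True retained levels are 100 and 70, so the difference becomes −30 − 0.3 × (70 v_L − 100 v_P).

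| v_P | v_L | Difference if kept |
|---|---|---|
| 5% | 5% | −30 − 0.3 × (3.5 − 5) = −29.55 |
| 10% | 10% | −30 − 0.3 × (7 − 10) = −29.1 |
| 20% | 20% | −30 − 0.3 × (14 − 20) = −28.2 |
| 5% | 15% | −30 − 0.3 × (10.5 − 5) = −31.65 |
| 15% | 5% | −30 − 0.3 × (3.5 − 15) = −26.55 |

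A simulation with correlation 0.6 between visits agrees (−29.4, −29.1, −28.3, −31.6, −26.5). In it, setting such values to missing leaves the difference near −30 in every case, with power of 81% to 83%. These are rates of invalid samples that were not repeated, and a repeat is required.

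**The case for a change.** The best argument for a change is that these rules decide which primary-endpoint values count, and that such rules should be explicit when the sponsor is unblinded. SAP 5.4 closes the deviation file before lock, so the omission here is not house style. SAP 5.7.2 applies the same vitamin C rule to supersaturation, so a secondary endpoint depends on it too. The all-data analysis covers neither baseline nor validity, and unequal rates of invalid samples, if kept, could move the estimate by 1.65 to 3.45 points. The remedy would be a few sentences.

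The textual observations stand: masking, finalisation and the lone invalid value are not stated, and the RBP cannot be assumed to cover masking. What does not stand is that following the plan gives an unsound result. Whether a product contains vitamin C is rarely a matter of judgement, and the review is done twice. SAP 4.4 defines baseline completely on its own terms, and the sensitivity analysis speaks of assessments after initiation of these medications, so extending Table 2 to screening is one reading and not the evident one. For a lone invalid sample, validity criteria that run throughout the study, medians of valid collections and no imputation all point an analyst to missing.

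**Conclusion.** No change is called for. These are details left unstated that analysts would fill sensibly, and at most they merit an optional wording note when the SAP is next opened.

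For the product review, plausible exclusions move an arm mean by about 0.4 to 2.4 points against a standard error of 10.1. The 4.9-point, 7.7% case needs selection by value that the rule does not provide for, and the planned all-data analysis would expose it. For baseline, a 30-point difference reads 29.0 to 30.0 under assumed shares of 1% to 10% and inflation of 11% to 50%, equal across arms.

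The lone invalid collection is the least certain part. Its size cannot be derived from the documents, and the 1.65 to 3.45 points shown rest on assumed unequal rates, 30% under-collection, and an analyst keeping values that the trial's own criteria call invalid. With the natural handling, missing, the estimate stays near 30.

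The conclusion assumes that required repeats are mostly obtained and that vitamin C content is read from product composition.
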